6.8.1 Continued follow up beyond 12-months post implant

Subjects on the treatment arm medication will be followed every six months after the 12-month follow up visit until the final ongoing subject reaches the 12 month visit or experiences a study outcome. Only treatment arm medication details, subject status (including death, withdrawal, or transplant) along with adverse events and device deficiencies will be collected along with additional supportive data should adverse events or device deficiencies occur. If a patient's clinical course after 12 months of follow up requires transition to open-label, the patient will be considered to have reached the end of study follow up unless the transition to open label is due to a stroke, in which case the patient should be followed for an additional 60-days to capture the MRS score. The clinical reason for transition to open-label will be captured. Subjects transitioned to open label prior to 12 months of follow up should be followed to their 12-month follow up.

6.9 Unscheduled Visits

6.9.1 Adverse Events

For additional details regarding adverse events, refer to section 7. Data related to adverse events will be collected as they occur. Depending on the type of adverse event, relevant data will be collected.

6.9.1.1 Neurologic Adverse Events

Modified Rankin Scores (MRS) scores will be captured at:

- Baseline,
- The time of any stroke or potential stroke events, and
- 60-days after any stroke or potential stroke events to adjudicate the severity of the event.

MRS will be determined by an independent assessor, defined as an independent, trained, and certified clinician. Event severity will be determined based on MRS, specifically MRS > 3 as disabling versus MRS ≤ 3 as nondisabling. Strokes will be characterized as ischemic or hemorrhagic in etiology with ischemic-hemorrhagic conversion considered an ischemic stroke.

6.9.2 Operative Procedures

Data related to any cardiac or non-cardiac operative procedures, excluding the primary HM3 LVAD implant, occurring after enrollment will be collected. Operative procedures must be reported to the Sponsor through the EDC system within three days of awareness of the event or, at the latest, if the operation is unknown to the implanting site (i.e. occurring at another facility), during the next follow-up visit. For pump exchanges, additional implant data will be collected, including exchange status and pump exchange type.

6.9.3 Hospitalizations

All hospitalizations, excluding the primary implant hospitalization, with associated reasons will be captured during the follow-up period for all subjects. While hospitalized, the follow-up visit assessments will continue to be performed according to the follow-up schedule. Hospitalizations must be reported to the Sponsor through the EDC system within three days of awareness or discovery of the event or, at the latest, if the hospitalization is unknown to the implanting site (i.e. occurring at another facility), during the next follow-up visit.

Clinical Investigation Plan

6.9.4 Outcomes

Subjects will be followed for at least 12 months and until the final ongoing subject reaches their 12 month visit or an outcome is reached, whichever occurs first. Outcomes include death, heart transplantation, device explant, and withdrawal from the study. Outcomes must be reported to the Sponsor through the EDC system immediately upon discovery of the event. Subjects should continue follow up through 12-months whenever possible, even in the instance the subject has transitioned to open-label (e.g. due to pump thrombosis the investigator believes the patient should remain on open-label aspirin therapy).

If a subject receives a pump exchange during the follow-up period, this event will be considered a device explant outcome and data will be collected on the pump exchange procedure but not after. If a subject has a device explanted for suspected or confirmed pump thrombosis, the pump will be returned to the Sponsor for analysis. Standard commercial processes will be used for pump return.

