3.0 CLINICAL INVESTIGATION DESIGN

This is a prospective, randomized, double-blinded, placebo-controlled clinical investigation of advanced heart failure patients treated with the HM3 with two different antithrombotic regimens: vitamin K antagonist with aspirin versus vitamin K antagonist with placebo. Subjects will be randomized in a 1:1 ratio.

Clinical Investigation Plan

The clinical investigation has been designed to involve as little pain, discomfort, fear, and any other foreseeable risk as possible for subjects. Refer to the Risks Analysis section of the clinical investigation plan for details.

The clinical investigation will be conducted at up to 50 centers worldwide. Greater than 50% of the patients enrolled in this study will be from centers based in the United States. The primary and secondary endpoints will be evaluated according to the statistical section (Section 8 and in the study statistical analysis plan; SAP). Outcomes for this study include death, transplant, withdrawal or pump exchange. All subjects, site, Clinical Events Committee (CEC), and sponsor personnel will remain blinded to the randomization scheme until the last ongoing study subject completes follow-up (specifically, experiences an outcome or has final study visit) and all data have been collected and adjudicated. Exceptions will be justified in the study blinding plan (e.g. DSMB). After a patient reaches 12-months of follow up, they will continue to be followed every 6-months, as long as they remain on the treatment arm medication, until the last ongoing patient reaches 12-months of follow up. Beginning at the 12-month follow-up visit, patients should be requisitioned two bottles of the treatment arm medication to cover the 6 months until the next follow up visit.

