5.4 Subject Enrollment

Once informed consent is obtained, subjects are considered enrolled. Subject data entry into the EDC will begin following enrollment into the clinical investigation. Subject data will be collected following enrollment to the clinical investigation until the subject is withdrawn, experiences an outcome (transplant, explant, exchange, or death), or completes study follow-up.

Subjects who provide informed consent and are subsequently found to not meet inclusion/exclusion criteria prior to randomization or otherwise do not proceed to randomization will be withdrawn in accordance with section 5.5 of this CIP. Subjects who experience a surgical adverse event prior to day 14 that requires investigator mandated antiplatelet therapy (either presence or absence) will be withdrawn and not included in the analysis population. Subjects who expire prior to day 14 will not be included in the analysis population. All patients considered for this study, including enrolled subjects not included in the analysis population, will be reported in the study consort diagram.

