5.5 Subject Withdrawal

If a subject does not meet all inclusion criteria, or meets at least one exclusion criteria after the subject is enrolled (consented), but prior to randomization, the subject will be considered a screen failure and withdrawn and will not be included in the analysis populations.

Those enrolled (consented) subjects that meet all inclusion criteria and no exclusion criteria post implant will be randomized within 2-7 days post-implant (the day of implant is day 0). However, if these subjects do not meet the randomization eligibility criteria, are not randomized, never start the treatment arm regimen, experience a surgical event (≤ 14 days post implant) that requires investigator mandated anti-platelet therapy or experience an outcome ≤ 14 days post implant then they will be withdrawn.

Each randomized subject shall remain in the clinical investigation until completion of the required follow-up period; however, a subject's participation in any clinical investigation is voluntary and the subject has the right to withdraw at any time without penalty or loss of benefit. Conceivable reasons for discontinuation may include, but not be limited to, the following:

- Subject outcome including death, transplant, or device explant or exchange
- Physician or subject voluntary withdrawal
- Subject lost-to follow-up as described below.

The Sponsor must be notified of the reason(s) for subject discontinuation. The site will provide this information to the Sponsor. Investigators must also report this to their respective IRB/EC as defined by their institution's procedure(s).

No additional follow-up will be required or data recorded from subjects once withdrawn from the clinical investigation, except for the reason and status at the time of withdrawal (deceased/alive). Subjects withdrawn from the study will cease treatment arm medication and be transitioned to an anticoagulation regimen in accordance with site standard of care by the investigator.

In case of subject withdrawal of consent, the site should make attempts to schedule the subject for a final clinical investigation visit. At this final follow-up visit, the following will be recorded, with the subject's permission:

- Subject status (deceased/alive)
- Any adverse event details prior to withdrawal of consent

Lost-to-Follow-up

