7.3 Adverse Event and Device Deficiency/Device Malfunction Reporting

7.3.1 Adverse Event Reporting

Safety surveillance and reporting starts as soon as the patient is enrolled in the clinical investigation. Adverse events occurring prior to randomization which disqualify a patient for randomization, but occur after consent, will be captured in the EDC and, if necessary, should be reported to the sponsor through standard commercial practices. Safety surveillance and reporting will continue until the last follow-up visit has been performed, the subject is deceased, the subject concludes participation in the clinical investigation or the subject withdraws from the clinical investigation. All adverse event, deaths, and device deficiency data will be collected throughout the time period defined above and will be reported to the Sponsor on a CRF. Additional information about an adverse event should be updated within the appropriate CRF. An offline form will be made available to allow the investigator to report SAEs in the event the entry cannot be made in the EDC. This offline form can be submitted by email to [contact]. This does not replace the EDC reporting system. All information must still be entered in the EDC system as soon as feasible.

Unchanged, chronic, non-worsening or pre-existing conditions are not AEs and should not be reported.

Abnormal laboratory values will not be considered AEs unless:

- the investigator determined that the value is clinically significant,
- the abnormal lab value required intervention, or
- the abnormal lab value required subject withdrawal from the clinical investigation, or
- the abnormal lab value meets the definition of an adverse event.

All adverse events will be collected on each subject throughout the follow up period – until the subject reaches an outcome or withdraws or until the study ends. Causes of death will be captured for all subjects who expire during follow up.

SAE Reporting

The investigator should report all SAEs to the Sponsor as soon as possible but no later than outlined below.

Clinical Investigation Plan

Clinical Site	Reporting timelines
All Sites	SAEs must be reported to the Sponsor no later than 3 calendar days from the day the site personnel became aware of the event or as per the investigative site's local requirements, if the requirement is more stringent than those outlined.

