2.3 Endpoint Analysis

2.3.1 Primary Endpoint

The primary endpoint is a composite of survival free of any non-surgical¹ major hemocompatibility related adverse event² at 1-year post implant.

¹ - Non-surgical – any event occurring > 14-days post implant.

² - Major Hemocompatibility Related Adverse Event:

- Stroke
- Pump Thrombosis (suspected or confirmed)
- Bleeding (including intracranial bleeds that do not meet the stroke definition)
- Arterial Peripheral Thromboembolism

A subject will be considered a success if they survive to their 12 month visit and have not experienced a non-surgical hemocompatibility related adverse events. Subjects who have an outcome (e.g. transplanted or explanted due to recovery) prior to their 12 month visit that have not reported a non-surgical hemocompatibility related adverse event prior to censoring will also be considered a success.

A subject will be considered a failure if:

- the subject expires prior to their 12 month visit
- the subject experiences a non-surgical hemocompatibility related adverse event prior to their 12 month visit.

The primary analysis will be performed using the mITT population.

[REDACTED]

[REDACTED]

[REDACTED]

[REDACTED]

Statistical Analysis Plan

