2.3.2 Secondary Endpoints

The secondary endpoints will be analyzed using the mITT population.

Non-surgical Major Hemorrhagic events: Hemorrhagic event rate per patient year will be calculated by dividing all non-surgical bleeding events and hemorrhagic stroke events by the cumulative years of study exposure. This rate will be compared between groups using Poisson regression.

Non-surgical Major Thrombotic events: The thrombotic event rate per patient year will be calculated by dividing the number of non-surgical ischemic strokes, pump thrombosis and arterial peripheral thromboembolic events by the cumulative years of study exposure. This rate will be compared between groups using Poisson regression.

Survival: The overall survival rate will be analyzed using a Kaplan-Meier analysis and the treatment groups compared using the log-rank test. Survival will be calculated starting at 14 days post implant.

Stroke Rate: The stroke rate will be calculated based on the number of strokes experienced by subjects, 14 days or more after device implant, and while on their treatment assignment, divided by the cumulative duration of study exposure (years of support). The treatment groups will be compared by using Poisson regression.

All strokes that occur 14 or more days after implant will be included, regardless of the treatment status of the subject (subjects who move off their randomized treatment will continue to be followed). Ischemic and hemorrhagic stroke rates and debilitating stroke rate (MRS > 3) will also be analyzed. The stroke rate and treatment comparison will be performed as described above.

Time to first non-surgical stroke event will also be analyzed using a Kaplan-Meier analysis. The treatment groups will be compared using a log-rank test.

Statistical Analysis Plan

Pump Thrombosis: The pump thrombosis rate will be calculated based on the number of suspected or confirmed pump thrombosis events experienced by the subject, 14 or more days post device implant, while on their treatment assignment divided by the cumulative duration of study exposure (years of support). The treatment groups will be compared by using Poisson regression.

All suspected pump thrombosis that occurs 14 or more days post implant will be included, regardless of the treatment status of the subject (subjects who move off their randomized treatment will continue to be followed). The pump thrombosis rate and treatment comparison will be performed as described above.

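### Deaths after a pump exchange are not recorded, so the secondary overall survival comparison is in effect survival on the original pump, with possibly informative censoring

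*Protocol*

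**What the plan says.** Protocol 6.9.4 covers a pump exchange during follow-up: "this event will be considered a device explant outcome and data will be collected on the pump exchange procedure but not after". Other sections agree:

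- Protocol 3.0: "Outcomes for this study include death, transplant, withdrawal or pump exchange". SAP 1.3 has the same list.
- Protocol 5.4 collects data until the subject is withdrawn, "experiences an outcome (transplant, explant, exchange, or death), or completes study follow-up".
- Protocol 5.5 gives among the reasons for discontinuation: "Subject outcome including death, transplant, or device explant or exchange". For withdrawn subjects it records only the reason and whether the subject was alive at that time.
- Protocol 7.3.1 collects adverse events "until the subject reaches an outcome or withdraws or until the study ends".

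SAP 2.3.2 defines the secondary survival endpoint: "The overall survival rate will be analyzed using a Kaplan-Meier analysis and the treatment groups compared using the log-rank test". It adds: "Survival will be calculated starting at 14 days post implant". The readable text gives no time horizon and no censoring rule for exchange, explant or transplant.

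In SAP 2.3.1 a subject fails the primary endpoint if "the subject expires prior to their 12 month visit", or after a non-surgical hemocompatibility event before that visit. A subject who reaches another outcome before month 12 with no such event is a success.

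**The concern.** Kaplan-Meier and the log-rank test assume that subjects who leave the risk set have the same later mortality as those who stay. That is doubtful for exchange. In Protocol Appendix II, both pump replacement and death appear among the events that may accompany a suspected device thrombus, so exchange and death lie on the same clinical path.

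The direction matters because the trial's hypothesis is that withdrawing aspirin does no harm to safety, and thrombosis is the natural harm to look for. If placebo led to more thromboses and exchanges, the deaths that followed would drop out mainly from the placebo arm, and the survival estimate would lean towards no difference.

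The protocol is also uneven here. Protocol 6.9.4 wants a subject who moves to open label because of pump thrombosis followed to 12 months where possible. A subject whose thrombosis leads to an exchange is not followed.

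**Working it through.** **What each analysis sees.** Take a subject with pump thrombosis on day 200, an exchange on day 203 and death on day 206.

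- Primary endpoint: failure on day 200, whatever happens next.
- Thrombotic-event rate and pump-thrombosis rate (SAP 2.3.2): the event counts in both.
- Overall survival: censored on day 203; the death is not required to be recorded.

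Now take a subject exchanged for another reason with no earlier event. Protocol 6.9.4 makes this an explant outcome, so SAP 2.3.1 makes the subject a success. A later death before month 12 would not be seen.

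**Inputs.** The plan states no figure on this point to reproduce. It gives no exchange rate and no mortality after exchange.

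- 628 randomised (Protocol 5.7), 1:1 (Protocol 3.0), so 314 per arm. The mITT set may be somewhat smaller.
- Two-year HM3 survival 79.0% and suspected pump thrombosis 1.4% (Protocol 1.1.1, the randomised HM3 versus HMII trial).
- Assumed: 50-100% of thromboses lead to exchange; 20-50% of exchanged subjects then die.

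**First-year deaths per arm**, constant hazard: 314 × (1 − √0.79) = 314 × 0.111 = 34.9.

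**Deaths lost per arm** = 314 × 1.4% × multiple × share exchanged × share dying.

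| Thrombosis rate | Thromboses per arm | Deaths lost (low to high) | Share of 34.9 |
|---|---|---|---|
| 1.4% | 4.4 | 0.4 to 2.2 | 1% to 6% |
| tripled | 13.2 | 1.3 to 6.6 | 4% to 19% |
| fivefold | 22.0 | 2.2 to 11.0 | 6% to 31% |

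The 1.4% is a two-year figure. Halved for one year (314 × 0.7% = 2.2 thromboses), the first row becomes 0.2 to 1.1 deaths, so that row is on the high side.

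**Effect on the hazard ratio.** Take the upper assumptions (all exchanged, half die), the rise on placebo only, and 34.9 other deaths in each arm.

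- Aspirin: 34.9 + 2.2 = 37.1 deaths.
- Placebo, tripled: 34.9 + 6.6 = 41.5. HR = ln(1 − 41.5/314) / ln(1 − 37.1/314) = 1.13.
- Placebo, fivefold: 34.9 + 11.0 = 45.9. HR = 1.26.

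In both cases the recorded deaths are 34.9 against 34.9, an apparent HR of 1.0.

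**Sensitivity of the test.** With 2 × 34.9 = 69.8 deaths, 80% power at two-sided 5% needs HR = exp[(1.960 + 0.842) / √(69.8 × 0.25)] = 1.96. Hidden ratios of 1.13 to 1.26 are far below that, so the gap would rarely change the log-rank result. It would shift the estimate.

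**The case against.** The strongest reply is that the harm path is already counted. Thrombosis after day 14 is a primary failure and enters two secondary comparisons, and death before month 12 is itself a primary failure. A rise in thrombosis large enough to matter for survival should show there. This stands, and it confines the problem to the secondary survival comparison and to event-free subjects exchanged for other reasons. For that second group the documents give no link to aspirin, so no imbalance between arms is shown.

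Some deaths may also surface. Data on the exchange procedure are collected, Protocol 7.3.1 asks sites to update reported events, and Protocol 10.8.3 has all deaths adjudicated. A death during or soon after the exchange may therefore be captured. That is partial capture, not a requirement, and it need not be complete or equal between sites.

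The missing-data section (SAP 2.7) is redacted and may contain a censoring rule. No such rule can restore deaths that were never collected.

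Transplant and explant end follow-up too. A remedy for exchange alone would leave survival mixing two kinds of follow-up unless the rule for the other exits is stated.

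**Conclusion.** The gap is real and small. Overall survival as planned is in effect survival on the original pump, with censoring at exchange that may be informative. At the cited thrombosis rate about 0.4 to 2.2 deaths per arm are lost; if thrombosis tripled on placebo, about 1.3 to 6.6. These figures rest on the assumed exchange share and mortality after exchange, on a constant hazard, and on a two-year thrombosis rate.

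A reader might infer more, and the documents do not support it:

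- That the trial would hide mortality from aspirin withdrawal, or that the primary result is compromised. Thrombosis is counted before any exchange.
- That this is the only comparison involving death. Death is in the primary composite; survival is the only standalone survival test.
- That an exchanged subject is counted as a survivor. Kaplan-Meier removes the subject from the risk set; the issue is whether that removal is informative.
- That the primary rule cannot classify an event-free exchanged subject. It does, as a success.
- That a large share of deaths would be lost whatever the treatment effect. That needs an exchange rate well above anything the documents give.

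**What to change.** - **Protocol 6.9.4, with 5.4, 5.5 and 7.3.1 to match:** record vital status, with date and cause of death, to month 12 post implant for every subject with a pump exchange, and preferably for every device exit. Adverse event and device data can still end at exchange.
- **SAP 2.3.2:** analyse 12-month overall survival without censoring at exchange. Report survival on the original pump as supportive. State the censoring rule for transplant and explant, and state the horizon, since some subjects are followed beyond month 12.
- **SAP 2.3.1:** leave the primary classification as it is, so that exchange is not treated differently from other exits. Add a sensitivity analysis that counts deaths after exchange and before month 12 as failures.

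The cost is a few vital-status checks (about 2 to 4 exchanged subjects per arm at the cited rate under the assumptions above, more if thrombosis rises or if all exits are included), matching edits in four protocol sections, and a check that the consent wording allows the contact. Some recorded deaths will reflect the exchange operation rather than the regimen. Treatment, visits and sample size do not change.
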